4.4.1.2 Secondary outcomes

Fasting blood sugar, HbA1C, cardiovascular events (heart failure admission, mortality), asthma control and blood pressure, hospitalizations and emergency visits measurements will be based on the clinics attended by the participants. Health care utilization, quality of life and health care expenditures will be measured for all the participants.

i. Data Collection

Data on patients' sociodemographic, resources consumptions such as direct and indirect medical costs and health quality of life (HRQoL) will be collected.

ii. Sociodemographic

Data such as socio-demographics (age, sex, education level, occupation, income, and religion), will be collected via face-to-face interview or phone interview via a structured and validated questionnaire.

iii. Direct Medical Cost

This study will apply a bottom-up micro costing approach for direct cost estimation. Healthcare costs such as outpatient visits, medicine use, hospitalization, diagnostic and laboratory test costs will be gathered in this study for direct cost estimation of chronic diseases. Costs for outpatient visits, hospitalization, diagnostic and laboratory tests will be valued based on the MOH Full Paying Patient Tariff Schedule of fees for a foreigner patient scheme provided by the Financial Department for Ministry of Health Hospitals. Medication utilization costs will be estimated from the National Price List of Medicines provided by the Procurement Unit of the Pharmacy Department. Costs of medicine per patient will be calculated by total drugs supplied for a patient multiplied by the average acquisition cost price obtained of the hospital. All costs will be valued in Malaysia Ringgit (MYR).

iv. Indirect Medical Cost

Indirect medical or patient out-of-pocket cost such as transportation costs, productivity losses, caregiver costs and waiting time in outpatient visit will be collected with the used of cost questionnaires to the participants. Patients will be requested to report the resource utilization over the past 3 months during the first time after recruitment(baseline) and after every 3 months (at 3 and 6 months). Transportation costs included parking fees. Patient time costs will be calculated based on waiting time in outpatient visit with the wages per hour of patient. Rate of wages per hour will be estimated based on patient's reported income per hour. Productivity losses will not be accounted for patients who are retired and jobless. This economic cost will help to evaluate the economic impact of CareAide from patients' perspective. All costs will be valued in Malaysia Ringgit (MYR).

v. Health-related quality of life (HRQoL) of patients

The overall health state and quality of life will be collected with the EuroQol-5D (EQ-5D-5L) and Short Form 36 Health Survey (SF-36) questionnaires to determine quality-adjusted life years (QALYS) over 3- and 6- months follow-up time. This study will use the EQ-5D-5L and SF-36 surveys to assess the HRQoL of chronic disease patients. The EQ-5D-5L instrument of the EuroQol is a validated tool to measure the health status of various groups in various diseases. This tool composed of five dimensions: mobility, self-care, usual activities, pain/discomfort and anxiety/ depression (Lins et. al., 2016). Another questionnaire SF-36 is a self-reported measure of health with 36 items which cover eight domains of health. The eight domains including vitality, mental health, physical functioning, bodily pain, general health perceptions, physical role functioning, emotional role functioning and social role functioning (Lins et al., 2016). Both tools consist of questionnaires whereas EQ-5D-5L consists of additional visual analogue scale. These tools will be conducted via face-to face or phone interview to assess the health status of respondents.

Trained research personnel will explain the purpose of the study and obtain consent of the participants before distributing or administering the questionnaires. Participants will then be distributed with questionnaires. EQ-5D-5L and SF-36 have different languages versions of the validated phone interview or face-to face questionnaires included English, Malay, Tamil and

Chinese languages for Malaysians. Research personnel will provide or use the patients' preferred version of language for conducting the survey.

[figure not shown]

Figure 1: Consolidated Standards of Reporting (CONSORT) flow chart (Consort, 2021; Evsenbach et. al., 2011).

4.4.2 Phase 2

Only the participants using the CareAide® app will be given the questionnaires at the end of 6 months follow up to understand the participant's perception of the perceived usefulness of the app and rate their satisfaction with the app. A structured questionnaire will be developed from existing literature (Kim et al., 2016; Eveleth & Robert, 2020) to facilitate data collection. It will be designed to be self-administered. The questionnaire will be divided into three sections to specify the type of questions to be asked. The first section consists of basic demographics, including age, gender, ethnicity, personal health status, and the number of medications taken. Section two includes the questions to explore the perception of the users towards the app. The responses will be measured using a 5-point Likert scale. Section three consists of a questionnaire to rate their satisfaction with the app.

For perception, the perceived usefulness questions were developed from the work of Kim et al., (2016), and the self-efficacy questions will be developed from Eveleth & Robert, (2020). The ratings will be given on a 5-point Likert scale. A higher rating corresponds to the higher agreement (e.g., 1=strongly disagree, 5=strongly agree).

For satisfaction, the satisfaction questionnaire will be an adaptation of the user satisfaction survey used in the mobile health (mHealth) apps by Melin et al. (2020). The questionnaire consists of 11 questions, 10 items where the respondent will be asked to rate to what extent they agree on each item on a 5-point Likert scale and concluded with an open question on the recommendation of any suggestions to customise the experience to the patient's needs.

Data will be collected via a self-administered questionnaire to explore the study participants' perceptions and satisfaction with the CareAide® app. The self-administered questionnaires will either be mailed or given in person to the respondents, and their participation is entirely voluntary. The content validity of the questionnaire will be assessed by a panel of experts based on their evaluation analysis through comments and feedback submitted. The questionnaire will be pilot tested on 20 patients to check the feasibility and validity of the questionnaire. Results from the pilot study will not be included in the final analysis. Should the respondents fail to understand and answer the questionnaire, modifications will be done to obtain accurate data. Cronbach's alpha test will be used to assess the internal consistency of the questionnaire.

Section 1: Participant demographics

Age group, gender, ethnicity, phone type, health status, education level, and number of medications taken

Section 2: Perception of perceived usefulness of the CareAide® app

- i. Improves medication adherence
- ii. Makes remote patient monitoring possible and easy
- iii. Improves the chance patients take their medications properly and on time - Excellent reminder to take or refill patient prescriptions and track pills remaining.
- iv. Improves social performance - Patients interaction with mobile apps (whether is clear and understandable)

- v. Practicality of technology for elderly (technology laggards, novice users or lack of comfort and familiarity with smartphones).

Section 3: Participant Satisfaction with the CareAide® app

a) What did you think about using the health app? (5-point Likert scale)

- It was easy to use
- It was good to use
- The time spent using it has been acceptable
- The introduction of how to use it was sufficient
- It was too time-consuming
- It was boring to use
- It was a disturbance/ distraction
- I will recommend it to others

b) Do you have any suggestions about how the app could do better and customise the experience for your needs?

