4.2 Participant Recruitment, Eligibility Criteria and Study Procedures

Patients will be recruited at the respective outpatient clinics. At the usual care clinic appointments, patients have their demographics and baseline data of blood pressure, blood sugar, basic blood profiles, asthma control and review of their disease management collected by consultants/researchers. Patients who meet the study criteria will then be instructed to see pharmacists/researchers at outpatient pharmacy to refill their medications. The pharmacists/researchers will screen patients' inclusion and exclusion criteria for this study and will explain that they may or may not be selected for the study and if they agree, proceed to provide written informed consent. The adherence data from the screening will be collected to gauge the general adherence rate in these group of patients. An independent researcher, who is not involved in the intervention and control groups, will use the random number function in Excel to generate randomisation sequences. The random numbers will be placed in opaque envelopes, which subsequently will be opened by pharmacists/researchers at the outpatient pharmacies. Participants and pharmacists/researchers are unblinded to group assignment and are aware of the intervention, but the study hypotheses are not disclosed to the participants. The assessor and statisticians are blinded to participant allocation. The study will be evaluating usual care compared with usual care plus pharmacist-driven patient-specific adherence interventions - CareAide® medication adherence digital application. Usual care provided by these hospitals comprises clinic appointments every 3 to 6 months.

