4.4.1.1 Primary outcome

Medication adherence: CareAide® effectiveness is measured with a medication adherence tool at baseline and follow-up time periods at 3 months and 6 months using Morisky Medication Adherence Scale-8 (MMAS-8) and proportion of days covered (PDC). The primary outcome of the study is medication adherence, which is assessed using the 8-item Morisky Medication Adherence Scale (MMAS-8) and the Proportion of Days Covered (PDC) method. Measurements are taken at baseline and at two additional time points, with a 3-month interval following the intervention. MMAS-8 is a licensed validated questionnaire to assess medication adherence, where a higher score represents higher medication adherence and vice versa. Comprising of 8 items, the score ranges from 0 to 8, where a higher score represents a higher medication adherence. The internal consistency (Cronbach's alpha) of MMAS-8 is 0.83 along with a sensitivity of 93% and a specificity of 57%. The PDC method utilises pharmacy refill records (Raebel et al., 2013). The PDC can be calculated as below (Hess et al., 2006; Raebel et al., 2013; Pednekar et al., 2019):

$Nm/Nd \times 100\%$

Where N_m denotes the number of days covered by the medication while N_d meant the number of days in the study period. The patients are considered to be adherent if their PDC scores are ≥ 0.8 or 80% (Karve et al., 2009). The prescription refill data was extracted from outpatient/hospital database.

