An economic evaluation will be conducted from a payer and societal perspective. Costs and outcomes will be discounted at 3% per year (Shafie et al., 2019) as the results will be extrapolated to examine costs and outcome over a year.. Cost effectiveness analysis will be estimated based on the results of cost data and EQ-5D-5L to calculate the incremental cost per quality adjusted life year (QALY) gained. Total incremental cost effectiveness ratio (ICER) will be calculated by dividing the difference between the cost of CareAide intervention group and control group by the difference between the QALYs of CareAide intervention group and control group. Sensitivity analysis will be performed by bootstrapping technique to ensure or examine the robustness of ICER. Then, cost effectiveness acceptability curve (CEAC) will be created to estimate the proportion of the result being cost-effective in relation to the Willingness-to-Pay (WTP) threshold.

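### With no stated baseline EQ-5D-5L and an unadjusted QALY difference, chance imbalance in starting utility enters the ICER and CEAC as avoidable variance

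*Combined protocol and SAP*

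**What the plan says.** **Where a baseline is named.**
- Adherence (section 4.4.1.1) is "measured with a medication adherence tool at baseline and follow-up time periods at 3 months and 6 months".
- Reported resource use (section 4.4.1.2, iv) is asked "during the first time after recruitment(baseline) and after every 3 months (at 3 and 6 months".
- Clinic measures (section 4.2) are "baseline data of blood pressure, blood sugar, basic blood profiles, asthma control and review of their disease management collected by consultants/researchers". HRQoL is not in that list.

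**Where it is not.** For EQ-5D-5L and SF-36, section 4.4.1.2(v) states only the purpose and horizon: "questionnaires to determine quality-adjusted life years (QALYS) over 3- and 6- months follow-up time". The same section says that consent is obtained and continues: "Participants will then be distributed with questionnaires". No visit is attached to that step. Figure 1, which follows directly, is not shown.

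**How QALYs are used.** Section 4.6 bases the analysis on "results of cost data and EQ-5D-5L to calculate the incremental cost per quality adjusted life year (QALY) gained". The cost difference is divided "by the difference between the QALYs of CareAide intervention group and control group". No rule is given for turning utilities into QALYs, and no adjustment for starting utility. The only HRQoL regression in section 4.6 looks for predictors of HRQoL. Bootstrapping and a CEAC are planned for uncertainty.

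**The concern.** A QALY is an area under the utility curve. Over six months with visits at 0, 3 and 6 months, the starting utility carries a quarter of the weight directly. It also predicts the later values, because utility is correlated within a person. If the arms differ by chance at the start, most of that difference reappears in the raw QALY difference as if it were an effect of the app.

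This matters more here than in most trials with a secondary economic analysis. Section 4.5 sets aside the sample size for adherence and sizes the trial on cost-effectiveness, with an expected QALY gain of 0.01. A gap of 0.02 in utility that persists for half a year yields that whole amount (0.02 × 0.5 = 0.01).

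The order of events is also open. Under section 4.2, pharmacists or researchers open the allocation envelopes at the outpatient pharmacy, and participants are unblinded. The plan does not say whether a baseline utility, if one is taken, comes before that step.

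**Working it through.** **1. Inputs from section 4.5.** Willingness to pay W = RM28,470 per QALY; ΔQ = 0.01; cost base RM2,499.15 with a 30% difference, so ΔC = 749.7; SdC = RM1,000; SdQ = 0.01; correlation 0.1; z-values 1.96 and 0.84; 200 patients with 20% attrition, so 200 × 0.8 / 2 = 80 per arm.

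**2. The plan's own figure.**
n = 2(1.96 + 0.84)² × [1000² + (28,470 × 0.01)² − 2 × 28,470 × 0.1 × 1000 × 0.01] / (284.7 − 749.7)²
= 15.68 × 1,024,114 / 465.0² = 74.3, rounded up to 75 per group. The stated figure reproduces, with the cost difference entered as positive and no price-index adjustment.

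**3. Weight of the starting utility.** With visits 0.25 year apart, the trapezoid rule gives Q = 0.125·u0 + 0.25·u3 + 0.125·u6. The weights sum to 0.5, and u0 holds 25% of them.

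**4. Under the plan's SdQ.** One SE of baseline imbalance moves the QALY difference by corr(Q, u0) × SdQ × √(2/80). Since the correlation cannot exceed 1, this is at most 0.01 × 0.158 = 0.0016 QALY, or about RM45. The limit is reached when utility is constant within a person, which implies a utility SD of 0.01/0.5 = 0.02.

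**5. Under assumed utility SDs.** The documents give none, so I take SD 0.10-0.25 and a common between-visit correlation r of 0.5-0.7 (compound symmetry). The slope of Q on u0 is 0.125 + 0.375r: 0.3125 at r = 0.5 and 0.3875 at r = 0.7. Shift for one SE = slope × SD × √(2/80). The last column is 2 × [1 − Φ(0.01/shift)].

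| SD | r | 1 SE of imbalance | QALY shift | RM | P(shift > 0.01) |
|---|---|---|---|---|---|
| 0.10 | 0.5 | 0.0158 | 0.0049 | 141 | 4% |
| 0.10 | 0.7 | 0.0158 | 0.0061 | 174 | 10% |
| 0.20 | 0.5 | 0.0316 | 0.0099 | 281 | 31% |
| 0.20 | 0.7 | 0.0316 | 0.0123 | 349 | 41% |
| 0.25 | 0.5 | 0.0395 | 0.0124 | 352 | 42% |
| 0.25 | 0.7 | 0.0395 | 0.0153 | 436 | 51% |

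These figures take u0 as measured and included in Q.

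**6. Gain from adjustment.** In units of SD², Var(Q) = 0.09375 + 0.15625r. Adjusting for u0 removes (0.125 + 0.375r)².
- r = 0.5: 0.1719 − 0.0977 = 0.0742. SE ratio √(0.0742/0.1719) = 0.66, a 34% reduction.
- r = 0.7: 0.2031 − 0.1502 = 0.0530. SE ratio √(0.0530/0.2031) = 0.51, a 49% reduction.

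The percentage does not depend on the utility SD. At SD 0.20 and 80 per arm, the SE of the QALY difference falls from 0.0131 to 0.0086 (r = 0.5) or from 0.0143 to 0.0073 (r = 0.7).

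**The case against.** **A baseline may well be intended.** The text leaves out the whole HRQoL schedule and does not limit it to 3 and 6 months. Questionnaires follow consent, section 4.4.1.2(i) lists costs and HRQoL as one data collection, and Figure 1 might show the visit. This stands. A reader might infer that no baseline exists, so that QALYs for the first three months cannot be calculated; the documents do not support that. An intended baseline would still not be used in section 4.6, and its order relative to allocation would still be unstated.

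**No upward bias follows from the plan.** A reader might also infer that the 3-month value would be carried back to month 0, crediting the app from the first day. The plan states no such method. Even without a baseline, giving both arms the same month-0 value yields a difference of 0.25·d3 + 0.125·d6, where d3 and d6 are the between-arm differences at 3 and 6 months. Under randomisation that is unbiased.

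**Chance imbalance is variance.** Bootstrapping and the CEAC already reflect it, so the unadjusted ICER is not invalid. This stands too. Resampling shows the uncertainty; it neither reduces it nor corrects the imbalance that occurred.

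**Costs drive the sizing.** In the plan's formula the QALY term is RM285 against RM750 for cost, so the net-benefit contrast of RM465 is the fairer yardstick. Against it, the shift is about RM45 under the plan's SdQ and RM141-436 under the assumed SDs.

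**SF-36 does not feed the ICER.** This is correct. Its timing matters only for describing HRQoL.

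**Conclusion.** The point holds as a cheap improvement to the economic analysis. No readable text gives EQ-5D-5L or SF-36 a baseline, and the ICER uses an unadjusted QALY difference. The consequence is avoidable variance and conditional bias from chance imbalance, not a systematic error in the ICER.

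Its size depends on a utility SD that the plan does not give. The effect is small if the plan's SdQ of 0.01 is right, and comparable to the planned 0.01 QALY if utility SDs are in the assumed range of 0.10-0.25. The 34-49% reduction in SE rests on compound symmetry with correlations of 0.5-0.7. All figures are for the six-month QALY with 80 per arm, before the extrapolation to one year in section 4.6.

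**What to change.** - **Section 4.4.1.2(v):** state that EQ-5D-5L, and SF-36 for HRQoL description only, are completed at baseline, 3 and 6 months in both arms, with the baseline completed before the allocation envelope is opened.
- **Section 4.6:** calculate QALYs by the trapezoid rule over 0, 3 and 6 months. Estimate the QALY difference by regression on arm and baseline utility. Refit that model within each bootstrap sample and use its estimate for the ICER and CEAC.

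The cost is a few sentences and, if a baseline is not already intended, a slightly longer baseline interview with instruments the trial already uses. The sample size does not change. The timing sentence should be settled before enrolment, because a utility not recorded before allocation cannot be recovered later.

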3.2 Secondary Objectives

1. To determine the clinical outcomes of CareAide® usage in patients with chronic diseases.
2. To evaluate and determine the cost-effectiveness of CareAide® in the management of chronic diseases in Malaysia.
3. To study and assess the burden and health-related quality of life (HRQoL) of chronic diseases for estimation of the quality adjusted life years (QALY).
4. To gauge the users' perception and satisfaction of the CareAide® application.

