4.0 Methodology

4.1 Study Design

A 3- and 6- month open-label multicentre randomized controlled trial with two parallel groups will be conducted. This study will take place in the outpatient setting of the three hospitals [i.e., Hospital Putrajaya, Hospital Pulau Pinang and Universiti Malaya Medical Center (UMMC)) in Malaysia]. Standard chronic disease treatments will be given to both groups of participants, but the CareAide ® app will be provided for the experimental group during the trial. Both groups will be allocated to 1:1 ratio. Randomization number will be generated by using online number generated programme. Consultants reviewing patients at medical, cardiology, diabetes mellitus and asthma clinics will provide referral and notify independent researchers for eligibility and group assignments. Eligible patients will then be instructed to see pharmacists/researchers at outpatient pharmacies to refill their prescriptions and subsequently enrol in the assigned study group either to receive an intervention with CareAide® or to receive normal clinical care. Information and training on the app will be provided by these researchers to the participants.

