4.2.1 Intervention group

- Intervention group will be asked to download and use the CareAide® app to help manage medications for 12 to 24 weeks. CareAide® is a free digital application designed to manage complex medicines schedules and improve adherence.

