4.2.2 Control group

- Control group will not be asked to download any digital applications but only receive the usual care by the hospitals.

4.3 Patients' inclusion and exclusion criteria are as follow:

4.3.1 Inclusion criteria:

- Age: 18 years and above
- Diagnosed with selected non-communicable diseases (NCDs): hypertension, diabetes mellitus, heart failure or asthma for at least 6 months
- Prescription generated from one of the following specialty clinics: Medical, Cardiology, Diabetes Mellitus or Asthma clinics
- Medications are prescribed in previous 3 months and refill at the point of recruitment
- Morisky Medication Adherence Scale (MMAS) score < 6
- More than three medications daily or two medications with multiple dosing intervals.
- One or more hospital admissions in the prior 24 months
- Understand and able to command in English and own a smartphone

4.3.2 Exclusion criteria:

- Medications prescribed from other institution providers
- Existing mobile health app or medication reminder app user
- Pregnant
- Cognitively impaired
- Prisoners
- Bed-bound
- Severe diseases/comorbidities – terminal cancer, psychiatry, etc

4.3.3 Withdrawal criteria:

Participants can choose to withdraw at any time for any reason, specified or unspecified, and without prejudice to their care. Participants may be withdrawn if the investigator feels that it is not for the participants' best interest to continue. The following is a list of possible reasons for study intervention discontinuation:

- Screening failure

- Participant withdrawal of consent
- Participant is not compliant with study procedures
- Protocol violation requiring discontinuation
- Lost to follow-up
- Request from sponsor for early termination of study
- Participant death

Withdrawn participants will not be replaced. It will be documented whether or not each subject completes the clinical study. If the Investigator becomes aware of any serious, related adverse events after the subject completes or withdraws from the study, they will be recorded in the source documents and on the Case Report Form (CRF). The Investigator will contact participants who are lost to follow-up. Contacts attempts with such subjects will be documented in the participant's records (e.g., times and dates of attempted phone contact, receipt for mailing a registered letter, etc.).

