4.6 Data Analyses

Intention to treat (ITT) analysis will be applied to evaluate the results to avoid any bias. The data analysis will be using the SPSS version 27. Data will be coded and analysed. Descriptive or categorical data will be expressed as mean \pm standard deviation (SD) unless otherwise stated. Student t-test will be used for analysis of normally distributed or continuous variables. Mann-Whitney test will be used for non-normally distributed data. Categorical data will be analysed using Chi-square or Fischer's exact test. A value of $P < 0.05$ is considered statistically significant.

The prevalence of medication compliant is quantified at 3 months and 6 months follow-up. Independent t-test or Mann-Whitney test will be used to compare MMAS score rankings between the intervention and control groups. Chi-Square test of independence will be used to determine the difference in number of patients with medication adherence between the intervention and control groups at 3 months and 6 months follow-up. Ordinal logistic regression, with the MMAS adherence score ranking, will be used to examine the association between intervention and control groups.

For the perception and satisfaction towards the app, the frequency and percentage of respondents in each category (strongly disagree to strongly agree) will be calculated. The median of each statement will then be calculated to give an overview of perception and satisfaction towards the CareAide® app. Chi-square, Mann-Whitney U, Kruskal Wallis, Chi-square tests and logistic regression will be used where appropriate. The open-ended question will be analysed using thematic analysis as proposed by Braun and Clarke (2012). Codes will be assigned to the data to describe the content. After the coding is completed, themes will be generated, reviewed, and named. Linear regression analysis will be conducted to determine the independent predictors of HRQoL.

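### As worded, the Phase 2 survey may miss participants who stopped the app or left the study early, so satisfaction would probably be overstated

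*Combined protocol and SAP*

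**What the plan says.** The survey serves the fourth secondary objective in section 3.2: "To gauge the users' perception and satisfaction of the CareAide® application". The Introduction (1.0) adds that the findings should help developers revise the app so that people keep using it.

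Section 4.4.2 (Phase 2) sets who is surveyed and when: "Only the participants using the CareAide® app will be given the questionnaires at the end of 6 months follow up". On delivery, the same section says: "The self-administered questionnaires will either be mailed or given in person to the respondents, and their participation is entirely voluntary". Section 4.6 describes the analysis: "the frequency and percentage of respondents in each category (strongly disagree to strongly agree) will be calculated".

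Other sections bear on who would be reached:

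- Section 4.1: the "app will be provided for the experimental group during the trial".
- Section 4.2.1: "Intervention group will be asked to download and use the CareAide® app to help manage medications for 12 to 24 weeks".
- Section 4.2.2: "Control group will not be asked to download any digital applications but only receive the usual care by the hospitals".
- Section 4.3.3 lists possible reasons for discontinuation. They include withdrawal of consent, loss to follow-up and "Participant is not compliant with study procedures".
- Section 4.5 settles on 200 patients, allowing for 20% attrition.

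**The concern.** Section 4.4.2 describes the survey population by a behaviour, using the app, and places the survey at one late time point. Elsewhere, when the plan means the randomised arm, it names the arm. If use is the condition for being surveyed, the sample is selected on something that happens after randomisation and is likely to be related to the answer. People who found the app burdensome or unhelpful are the likeliest to have given it up.

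What is at stake is the usefulness of secondary objective 4. A developer who wants to know why people stop cannot learn it from a sample that leaves out those who stopped. A published satisfaction percentage could also look better than the experience of everyone who tried the app.

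**Working it through.** **Step 1. The wording, under two readings.**

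*Reading A: use at month 6 is required.* Participants who gave up the app are excluded. So are those whose planned use had simply ended. Section 4.2.1 plans 12 to 24 weeks of use, while 6 months is about 26 weeks (52 / 2). Even the longest planned use ends about 26 − 24 = 2 weeks before the survey.

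*Reading B: the phrase means the app arm, as opposed to controls.* Participants who stopped the app but stayed in follow-up are then included. The questionnaire is still given only at the end of follow-up, so participants discontinued early under section 4.3.3 have no stated route to it. If 200 are enrolled 1:1, the app arm has 200 / 2 = 100 people. If the 20% attrition in section 4.5 falls equally on both arms, that is 100 × 0.20 = 20 people. This is study attrition, which is not the same as stopping the app.

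Under both readings section 4.6 reports percentages of respondents. It states no survey denominator, no count of people who stopped and no handling of non-response. Its general intention-to-treat sentence does not say how that principle would apply to the survey.

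**Step 2. Size.** The plan gives no survey sample size, response rate, stopping rate or expected satisfaction, so there is no figure of its own to reproduce. What follows is an illustration with assumed values.

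Among those who opened the app, let *q* be the share who stopped and are not surveyed, *S_c* the proportion satisfied among continuing users, and *S_s* the proportion satisfied among those who stopped. Assume that every continuing user responds.

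- The survey reports *S_c*.
- The figure for everyone who opened the app is (1 − *q*) × *S_c* + *q* × *S_s*.
- Overstatement = *q* × (*S_c* − *S_s*).

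Example with *S_c* = 80%, *S_s* = 40%, *q* = 20%: 0.80 × 0.80 + 0.20 × 0.40 = 0.64 + 0.08 = 0.72. The survey reports 80% against 72%, an overstatement of 8 points, which is 0.20 × 0.40.

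Overstatement in percentage points, with *S_c* = 80% throughout (figure for everyone who opened the app in brackets):

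| Share stopped | *S_s* = 80% | *S_s* = 60% | *S_s* = 40% | *S_s* = 20% |
|---|---|---|---|---|
| 10% | 0 (80%) | 2 (78%) | 4 (76%) | 6 (74%) |
| 20% | 0 (80%) | 4 (76%) | 8 (72%) | 12 (68%) |
| 50% | 0 (80%) | 10 (70%) | 20 (60%) | 30 (50%) |

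Under Reading B, if the 20 people above had all opened the app and none were surveyed, the 20% row applies.

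**The case against.** The strongest reply is that section 4.4.2 does not say *still using*. The 6 months can be read as the timing of the survey, with no requirement of use at that date. Controls have no app to rate, so the restriction may only mark the app arm off from the control arm. The satisfaction items support this: most are in the past tense, several are negative (time, boredom, distraction), and a former user could answer them. On the strict reading, someone who completed a planned 12 weeks of use would be shut out at month 6, which the authors are unlikely to have wanted. The withdrawal link is also an inference. Section 4.3.3 lists possible reasons and does not say that giving up the app counts as non-compliance.

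Much of this stands. The app-arm reading is plausible and perhaps the more natural one. A reader might infer that the survey is confined to people still using the app at month 6 and that satisfaction is therefore overstated; the documents establish neither. Overstatement needs two things: that people who stopped are missed, and that they are less satisfied. The second is likely but not shown. If they are equally satisfied, the overstatement is zero.

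The reply does not close the gap. No section says that people who stopped will be surveyed, and even on the app-arm reading those discontinued early have no stated way to receive the questionnaire. The past-tense items show that former users could be surveyed with the same instrument; they do not show that they will be.

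**Conclusion.** The point holds as a weakness in who is surveyed and when. *Using* is undefined, and there is no stated route to the survey for people who stopped the app (on the strict reading) or were discontinued early (on either reading). The likely direction is overstated satisfaction. The size cannot be derived from the documents: under the assumed rates it is 0 to 12 points with 20% stopping and 0 to 30 points with 50% stopping. Those ranges are not evidence about this trial. The firmer claim, that the plan samples only continuing users and so does overstate satisfaction, goes beyond the text.

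The consequence is limited. This is a secondary, descriptive objective, and the adherence and economic comparisons do not depend on it. It is a worthwhile improvement and not a threat to the trial.

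**What to change.** In section 4.4.2, replace the eligibility wording with: all participants randomised to CareAide who opened the app at least once, including those who stopped using it or were discontinued from the study and who still consent to contact. Give the questionnaire at 6 months, or at discontinuation for those who leave the study early, using the mail route already planned. The satisfaction items need little or no change.

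In section 4.6, add that the report will give the numbers allocated to CareAide, never opened, stopped and responding, with results shown separately for continuing and stopped users. Those who never opened the app cannot rate it; they are counted but not surveyed, so the satisfaction denominator matches the population surveyed.

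The cost is a few extra mailed questionnaires and one extra table. Assessment times will be somewhat mixed, because some people answer before 6 months; the split table should show this. Satisfaction figures may come out lower. The change should be made before survey collection starts, since people who have left may be hard to reach later.
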